# 1 Prelude

The scientific community has responded to the COVID-19 pandemic with admirable global cooperation and solidarity, characterized by rapid sharing of results and data in an effort to urgently re-focus research toward the common goal of developing prevention and treatment modalities to help turn the tide of the COVID-19 pandemic. As spoken by WHO Director-General [name] Ghebreyesus at the 2020 Aspen Security Forum, "Our best way forward is to stick with science, solutions and solidarity and together we can overcome this pandemic." World Health Organization (2020)

In this spirit, we are making this Statistical Analysis Plan (SAP) publicly available at a relatively early and intermediate stage. The SAP is a work in progress that will continue to be developed and refined over the coming weeks. Our hope is that fellow statistical scientists and scientists of other disciplines will bring new insights and offer input to maximize the scientific knowledge pertaining to immune correlates of protection that can be learned from COVID-19 vaccine efficacy trials. We invite collaboration and are eager to explore opportunities for working with others on COVID-19 immune correlates analyses.

We envisage three applications of this SAP. First, as the Coronavirus Prevention Network Statistical Center and COVID-19 Response Biostatistics Team our group is responsible for statistical design and analysis of immune correlates for the United States Government (USG)/COVID-19 Response Team phase 3 trials, and this SAP serves as a master protocol-type SAP for harmonized immune correlates analyses across the trials. Second, researchers conducting additional clinical trials may work collaboratively with our group to co-conduct the immune correlates analysis. Third, researchers conducting clinical trials may use this SAP as a resource for immune correlates analyses conducted on their own, either by implementing this SAP or components therein, or by selecting methods and code from it to adopt for their own SAPs.

We are implementing the SAP in R. The R scripts are hosted on a Github code repository CoVPN/correlates\_reporting and will be made publicly avail-

able as soon as they are ready. The first publicly available download will be focused on immunogenicity characterization and correlates of risk analysis and the second one will be focused on correlates of protection analysis. This collaborative Github repository will include reproducible reports implementing the SAP on a mock/practice COVID-19 vaccine efficacy trial data set.

Please direct communication related to this SAP to [name] at the Fred Hutchinson Cancer Research Center ([contact]).

# 2 Introduction

## 2.1 Antibody Assays and Day 57 Markers

This SAP describes the statistical analysis of antibody markers measured at a key time point post last vaccination as immune correlates of risk and as various types of immune correlates of protection against primary and secondary endpoints in COVID-19 Response Team / CoVPN COVID-19 vaccine efficacy (VE) trials. For definiteness, we assume this time point for antibody measurements is Day 57, a typical time point for a two-dose vaccine; for a one-dose vaccine the key time point would likely be around Day 29. The antibody markers of interest are measured using one of three kinds of humoral immunogenicity assays [more detail on assay types (2) and (3) can be found in Sholukh et al. (2020)]:

(1) **bAbs**: **Binding antibodies** to the vaccine insert SARS-CoV-2 proteins;

(2) **Pseudovirus-nAbs**: **Neutralizing antibodies** against viruses **pseudotyped** with the vaccine insert SARS-CoV-2 proteins; and

(3) Wild Type Live virus-nAbs: Neutralizing antibodies against live "vaccine insert-matched" wild type SARS-CoV-2 (or recombinant "vaccine insert-matched" SARS-CoV-2 harboring a reporter gene within the viral genome).

For example, the following assays are expected to be used:

(1) **bAb assay**: The MSD-ECL Multiplex Assay (MSD-ECL = meso scale discovery-electrochemiluminescence assay)

The MSD assay measures binding antibody to antigens corresponding to: Spike (an engineered version of the Spike protein harboring a double proline substitution (S-2P) that stabilizes it in the closed, prefusion conformation [McCallum et al. (2020)]); the Receptor Binding Domain (RBD) of the Spike protein; and Nucleocapsid protein (N), which is not contained in any of the COVID-19 vaccines.

This assay has a standard curve to interpolate arbitrary units/ml; an 8 point dilution curve on each sample with 5-fold dilutions starting at 1:20; an 8 point dilution curve on VRC control sera; and includes Positive, Negative and Intermediate controls. Binding antibody to N are not of interest as a potential immune correlate; these data are included only for immunogenicity evaluation. Based on the starting dilution of the standards and samples at 1:20, the lower limit of detection (LLOD) for the endpoint titer of the assay is 1:20. Binding antibody readouts below the LLOD are assigned the value LLOD/2 = 10. Values between the LLOD and the lower limit of quantitation (LLOQ) are taken as their actual numeric value.

The bAb assay readouts are in units AU/ml, where AU stands for arbitrary units from a standard curve. The process of validating the assay defined a lower limit of detection (LLOD), an upper limit of detection (ULOD), a lower limit of quantitation (LLOQ), an upper limit of quantitation (ULOQ), and a positivity cut-off for each antigen that defines positive vs. negative response. These values are as follows:

- bAb Spike:
  - Pos. Cutoff = 1204.71 AU/ml
  - LLOD = 34.18 AU/ml
  - ULOD = 19,136,250 AU/ml
  - LLOQ = 199.64 AU/ml
  - ULOQ = 1,128,438.87 AU/ml
- bAb RBD:
  - Pos. Cutoff = 517.86 AU/ml

- LLOD = 58.59 AU/ml
- ULOD = 8,201,250 AU/ml
- LLOQ = 125.9678 AU/ml
- ULOQ = 598,133.3615 AU/ml

• N:

- Pos. cutoff = 9779.62 AU/ml
- LLOD = 39.06 AU/ml
- ULOD = 21,870,000
- LLOQ = 1870.70 AU/ml
- ULOQ = 239,449.31

The Vaccine Research Center established factors for converting the MSD assay readouts from AU/ml to WHO International Units/ml, which is the same thing as Binding Antibody Units/ml (BAU/ml). For the three binding antibody variables CoV-2 Spike IgG, CoV-2 RBD IgG, and CoV-2 N IgG, these conversion factors are 0.0090, 0.0272, and 0.0024, respectively. These conversion factors are applied, such that all binding Ab readouts are reported in WHO International Units/ml with notation BAU/ml, following the WHO recommendation, for all analyses. These conversion factors are also applied to yield the LLOD, ULOD, LLOQ, and ULOQ on the WHO BAU/ml scale. The following shows the assay limits on the BAU/ml scale:

- bAb Spike:
  - Pos. Cutoff = 10.8424 BAU/ml
  - LLOD = 0.3076 BAU/ml
  - ULOD = 172,226.2 BAU/ml
  - LLOQ = 1.7968 BAU/ml
  - ULOQ = 10,155.95 BAU/ml
- bAb RBD:

- Pos. Cutoff = 14.0858 BAU/ml
- LLOD = 1.593648 BAU/ml
- ULOD = 223,074 BAU/ml
- LLOQ = 3.4263 BAU/ml
- ULOQ = 16,269.23 BAU/ml
- bAb N:
  - Pos. Cutoff = 23.4711 BAU/ml
  - LLOD = 0.093744 BAU/ml
  - ULOD = 52,488 BAU/ml
  - LLOQ = 4.4897 BAU/ml
  - ULOQ = 574.6783 BAU/ml

All values below the LLOD are assigned the value LLOD/2. For immunogenicity reporting, values greater than the ULOQ are not given a ceiling value of the ULOQ, the actual readouts are used. For the immune correlates analyses, values greater than the ULOQ are assigned the value of the ULOQ.

(2) **Pseudovirus-nAb assay**: A firefly luciferase (ffLuc) reporter neutralization assay for measuring neutralizing antibodies against SARS-CoV-2 Spikepseudotyped viruses

Based on the Duke assay from the [name] lab, serum inhibitory dilution 50% titer (ID50) and serum inhibition dilution 80% titer (ID80) values are estimated based on a starting serum dilution of 1:10, with eight 5-fold dilutions. Thus 1:10 is the LLOD on the scale of the assay. The process of validating the assay defined the LLOD, LLOQ, and ULOQ for ID50 and ID80 as follows:

- ID50:
  - LLOD = 10 - LLOQ = 18.5

$$-\mathrm{ULOQ} = 45118$$

- ID80:
  - LLOD = 10
  - LLOQ = 14.3
  - ULOQ = 10232

ID50 and ID80 values below the LLOD are assigned the value 10/2 = 5. Values between the LLOD and the LLOQ are taken as their actual numeric value. For immunogenicity reporting, values greater than the ULOQ are not given a ceiling value of the ULOQ, the actual readouts are used. For the immune correlates analyses, values greater than the ULOQ are assigned the value of the ULOQ. This is done so as to not unduly influence the correlates analyses by high outlying values, given the expectation that the most relevant marker dynamic range for correlates is much lower than the ULOQ.

ID50 and ID80 values are reported in international units based on the report from [name] "Reagent Calibration Report: First WHO International Standard for SARS-CoV-2 Immunoglobulin in a Neutralization Assay" (May, 2021). This report derived calibration factors based on arithmetic means:

- Calibration factor ID50: 0.242
- Calibration factor ID80: 1.502

The original readouts are calibrated to the IU scale by multiplying each original ID50 value by 0.242, and multiplying each original ID80 value by 1.502, and units are reported as calibrated ID50 (cID50) and calibrated ID80 (cID80). Consequently, the LLOD, LLOQ and ULOQ for cID50 and cID80 are as follows in International Units:

• cID50:

- LLOD = 2.42
- LLOQ = 4.477
- ULOQ = 10919

- cID80:
  - LLOD = 15.02
  - LLOQ = 21.4786
  - ULOQ = 15368

(3) Wild Type Live virus-nAb assay: An assay measuring antibodymediated neutralization of live wild-type SARS-CoV-2 (WA isolate, passage 3, Vero-E6 cells).

The WT live virus-nAb marker is defined as MN50 calculated using the Spearman-Karber method. The Battelle assay has the following parameters, in original MN50 units and in International Units (IU) with WHO IU conversion factor 0.276:

- LLOD: 82.11 MN50 (22.66 IU)
- LLOQ: 159.79 MN50 (44.1 IU)
- ULOQ: 11,173.11 MN50 (3,083.74 IU)

Values below the LLOD are assigned the value LLOD/2. Values between the LLOD and the LLOQ are taken as their actual numeric value. Values greater than the ULOQ are assigned the value of the ULOQ.

Throughout this SAP we assume that all three types of assays have validated versions that are applied uniformly to samples collected in one or several late-stage SARS-CoV-2 vaccine efficacy trials. Samples from the same trial are expected to be assayed by the same lab that performs one of these immunoassays.

Based on each immunoassay applied to paired serum samples collected from participants on Day 1 (baseline, pre-vaccination) and Day 57 (post-vaccination visit), the following set of antibody markers is defined for immunogenicity and immune correlates analyses.

• For bAb:  $\log_{10}$  IgG concentration (BAU/ml) at each time point, and the difference in  $\log_{10}$  concentration (Day 57 minus Day 1) representing  $\log_{10}$  fold-rise in IgG concentration from baseline to 28 days post dose two. These markers are defined for each antigen Spike, RBD, and N.

- For PsV nAb:  $\log_{10}$  serum inhibitory dilution 50% titer (ID50) and serum inhibition dilution 80% titer (cID80) at each time point, as well as the  $\log_{10}$  fold-rise of these markers over Day 1 to Day 57.
- For WT live virus nAb:  $\log_{10}$  serum MN50 at each time point, as well as the  $\log_{10}$  fold-rise of this marker over Day 1 to Day 57.

For two-dose vaccines, the immunogenicity and correlates analyses may also include the same antibody markers measured at the second-dose sampling time point, which we refer to as the Day 29 time point. In this SAP we include contingency sub-sections marked '[With Day 29 Markers]' to describe how the SAP is augmented to include the Day 29 antibody markers in the analysis.

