Neutralization responders at each pre-defined timepoint are defined as participants who had baseline values below the LLOD with detectable ID50 neutralization titer above the assay LLOD, or as participants with baseline values above the LLOD with a 4-fold increase in neutralizing antibody titer. Neutralization 2FR (4FR) at each pre-defined timepoint are defined as participants who had baseline values below the LLOQ with ID50 at least 2 times (4 times) above the assay LLOQ, or as participants with baseline values above the LLOQ with at least a 2-fold (4-fold) increase in neutralizing antibody titer. While quantitative fold-rise is shown for both ID50 and cID80, response above LLOD, 2FR and 4FR responder status are shown only for ID50. (However, for superlearner analysis of multivariable CoRs, 2FR and 4FR responder status variables are included for each of pseudovirus-nAb ID50 and cID80, given the objectives of more comprehensive analysis in building the estimated optimal surrogate.)

For WT live virus-nAb MN50, the same types of variables are analyzed/reported as for pseudovirus-nAb ID50.

Note that for defining positive response, 2FR, and 4FR, a reason why values below the LLOD are set to half the LLOD before calculating the indicator of response, is to ensure that a vaccine recipient that has an unusually low antibody readout at baseline and a post-vaccination value below or near the LLOD is not erroneously counted as a responder.

The following list describes the antibody variables that are measured from immunogenicity subcohort and infection case participants.

- 1. Individual anti-Spike antibody concentration at each pre-defined time point
- 2. Individual anti-Spike antibody fold-rise concentration post-vaccination relative to baseline at each pre-defined post-vaccination time point
- 3. Individual anti-RBD antibody concentration at each pre-defined time point
- 4. Individual anti-RBD antibody fold-rise post-vaccination relative to baseline at each pre-defined post-vaccination time point
- 5. Individual anti-N antibody concentration at each pre-defined time point
- 6. Individual anti-N antibody fold-rise post-vaccination relative to baseline at each pre-defined post-vaccination time point
- 7. 2-fold-rise and 4-fold rise (fold rise in anti-Spike antibody concentration [post/pre]  $\geq$  2 and  $\geq$  4, 2FR and 4FR) at each pre-defined postvaccination time point

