- 8. 2-fold-rise and 4-fold rise (fold rise in anti-RBD antibody concentration [post/pre]  $\geq$  2 and  $\geq$  4, 2FR and 4FR) at each pre-defined postvaccination time point
- 9. 2-fold-rise and 4-fold rise (fold rise in anti-N antibody concentration  $[post/pre] \ge 2$  and  $\ge 4$ , 2FR and 4FR) at each pre-defined post-vaccination time point
- 10. Pseudovirus-nAb responders, at each pre-defined timepoint defined as participants who had baseline values below the LLOQ with detectable pseudovirus-nAb ID50 titers above the assay LLOQ or as participants with baseline values above the LLOQ with a 4-fold increase in pseudovirus-nAb ID50 titers
- 11. Wild type live-virus-nAb responders, at each pre-defined timepoint de-

fined as participants who had baseline values below the LLOQ with detectable WT live virus-nAb MN50 titers above the assay LLOQ or as participants with baseline values above the LLOQ with a 4-fold increase in WT live virus-nAb MN50 titers

Summaries of the immunogenicity data will be reported in tables. In particular, the tables will include, for each pre-defined post-baseline time point:

1. For each binding antibody marker, the estimated percentage of participants defined as responders, and with concentrations  $\geq 2x$  LLOQ or  $\geq 4 \times LLOQ$ , will be provided with the corresponding 95% CIs using the Clopper-Pearson method.

In addition, the estimated percentage of participants defined as responders, participants with 2-fold rise (2FR), and participants with 4-fold rise (4FR) will be provided with the corresponding 95% CIs using the Clopper-Pearson method.

- 2. For the ID50 pseudo-virus neutralization antibody marker, the estimated percentage of participants defined as responders, participants with 2-fold rise (2FR), and participants with 4-fold rise (4FR) will be provided with the corresponding 95% CIs using the Clopper-Pearson method
- 3. For the MN50 WT live virus neutralization antibody marker, the estimated percentage of participants defined as responders, participants with 2-fold rise (2FR), and participants with 4-fold rise (4FR) will be provided with the corresponding 95% CIs using the Clopper-Pearson method

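### MN50 is capped at its ULOQ with no exception for immunogenicity reporting, unlike the other assays; this lowers GMTs and fold-rises and makes a 4-fold rise impossible from a baseline above 2,793

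*Combined protocol and SAP*

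**What the plan says.** All three ULOQ rules are in SAP Section 2.1.

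- **Binding antibody and pseudovirus ID50/ID80.** Two uses are separated. The first is uncapped: "For immunogenicity reporting, values greater than the ULOQ are not given a ceiling value of the ULOQ, the actual readouts are used". The second is capped: "For the immune correlates analyses, values greater than the ULOQ are assigned the value of the ULOQ". The reason given, in the pseudovirus paragraph, is to keep high outlying values from unduly influencing the correlates analyses.
- **Live-virus MN50.** There is one sentence with no restriction by use: "Values greater than the ULOQ are assigned the value of the ULOQ". Shortly afterwards the section states that "the following set of antibody markers is defined for immunogenicity and immune correlates analyses", so the preceding rule reads as covering both uses.

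Section 9.1.1 says that for MN50 "the same types of variables are analyzed/reported as for pseudovirus-nAb ID50", without mentioning the ceiling. Its list of variables counts as MN50 responders, besides those who go from below to above the LLOQ, "participants with baseline values above the LLOQ with a 4-fold increase in WT live virus-nAb MN50 titers". Section 9.2 repeats that definition. No section exempts MN50 from the cap in immunogenicity reporting.

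**The concern.** The SAP's reason for capping concerns correlates analyses only, so it does not support capping MN50 in immunogenicity tables. A programmer who follows the text would cap MN50 everywhere and leave the other assays uncapped in the same tables.

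The outputs at stake are planned ones. Section 9.1.1 calls for MN50 responder, 2FR and 4FR rates, GMTs, and ratios to baseline and to Day 57. It also lists baseline-positive vaccine vs placebo and baseline-negative vs baseline-positive vaccine. Section 3.1 assigns baseline-positive data to immunogenicity characterization. In Table 5, 50 per stratum × 6 strata × 2 arms = 600 of the 1,620 planned subcohort members are baseline positive, with equal arms so that antibody responses in previously infected people can be compared. A ceiling on MN50 acts most on the group with the highest titers.

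**Working it through.** **Inputs from the SAP (Section 2.1).** MN50 LLOD 82.11, LLOQ 159.79, ULOQ 11,173.11; conversion factor 0.276. Check of the plan's own figure: 11,173.11 × 0.276 = 3,083.78 IU, against 3,083.74 stated, which agrees to about 0.001%.

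**Step 1: responder limits.** With the later value capped, the highest baseline that can show a k-fold rise is ULOQ/k.

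- 4-fold (responder and 4FR): 11,173.11/4 = 2,793.
- 2-fold (2FR): 11,173.11/2 = 5,587.

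Both lie far above the LLOD and the LLOQ, so the fold-rise branch of the definition applies whichever limit is used. Example: 3,000 rising to 30,000 is 10-fold, but is recorded as 11,173.11/3,000 = 3.72-fold, a non-responder.

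For a participant below the LLOQ at baseline, response means exceeding 159.79, and 2FR and 4FR mean reaching about 320 and 639. The cap changes none of these calls.

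**Step 2: GMT.** The GMTs are assumptions. The SD of 0.94 is the Section 24.2.1 default for Day 57 MN50 in mock data, and 0.7 is a lower alternative. For normal log10 titers with k = (log10 ULOQ − log10 GMT)/SD, capping lowers the log10 mean by e = SD × [φ(k) − k(1 − Φ(k))].

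Example, SD 0.94 and GMT 3,000: k = (4.048 − 3.477)/0.94 = 0.61, e = 0.157, and 10^(−0.157) = 0.70, so the GMT is 30% low.

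| Assumed GMT | Above ULOQ, SD 0.94 | GMT low by, SD 0.94 | GMT low by, SD 0.7 |
|---|---|---|---|
| 300 | 5% | 4% | 1% |
| 958 | 13% | 13% | 4% |
| 3,000 | 27% | 30% | 17% |

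Simulation with values below the LLOD set to half the LLOD gives the same percentages. At an assumed SD of 0.4 and GMT of 500, only 0.04% exceed the ULOQ and the loss is about 0.01%.

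**Step 3: ratios.**

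- Baseline-negative over baseline-positive vaccine, assumed GMTs 300 and 3,000: 0.118 becomes 0.162 at SD 0.94. The uncapped value is not exactly 0.1 because low values are set to half the LLOD.
- Post-Day 57 over Day 57 under waning, assumed GMTs 500 and 3,000: 0.167 becomes 0.172 to 0.222 for SDs of 0.4 to 0.94.
- Rises from baseline shrink, as in Step 1.

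These ratios all move toward 1; they do not all move down.

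**Step 4: misclassified baseline positives.** Simulated with baseline SD 0.8 (mock-data default), Day 57 SD 0.94 and assumed correlations of 0.3 to 0.7. The last two columns count people with a true rise of at least 4-fold who are called non-responders under the cap, as a share of all baseline positives.

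| Assumed baseline GMT | Start above 2,793 | Misclassified, Day 57 GMT 3,000 | Misclassified, Day 57 GMT 10,000 |
|---|---|---|---|
| 200 | 8% | 2.5–5% | 4–7% |
| 500 | 18% | 5–8% | 8–13% |
| 1,000 | 29% | 6–10% | 12–18% |

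**The case against.** The strongest reply is that this is a drafting omission. Section 9.1.1 treats MN50 like ID50, and the Prelude calls the SAP a work in progress. Alternatively the cap may be deliberate: the SAP gives no MN50 dilution series or upper limit of detection, so a reader cannot tell whether usable readouts above the ULOQ exist. Both are possible. Neither removes the problem, because the text as it stands caps MN50 and does not say how fold-rise status is handled near the ceiling.

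Other limits stand in full. Every assay is capped for correlates, so the SAP's main analyses are untouched. Section 12.4.2 allows for MN50 being absent from the first correlates data set. Baseline-negative participants, whose Day 1 readouts are expected to be generally negative, keep their responder calls. The SDs are defaults for mock data, and the GMTs and correlations are assumptions.

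Three stronger readings are tempting and are not supported:

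- **All MN50 ratios are biased low.** Step 3 shows planned ratios that rise.
- **The 8%, 18% and 29% who start above 2,793 are all misclassified.** Many of them would not rise 4-fold without a cap; only those who would are miscalled.
- **MN50 is the assay most affected, because its range is narrowest.** Its LLOD-to-ULOQ range is log10(11,173.11/82.11) = 2.13, against log10(45,118/10) = 3.65 for ID50. What matters is the share of readouts above the ULOQ, which the documents do not give for any assay.

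**Conclusion.** The MN50 rule is wrong as written; severity is minor. The limits of 2,793 and 5,587 are exact consequences of the text and need no assumption about titers. The downward effect on GMTs and rises from baseline, and the general pull of other ratios toward 1, occur only to the extent that readouts exceed 11,173.11. If few do, the effect is negligible.

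The illustrated sizes are a GMT 1% to 30% low, and 2.5% to 18% of all baseline positives miscalled as non-responders. They hold only under the GMTs, SDs and correlations stated above and are not estimates for the trial. The consequence is confined to MN50 immunogenicity tables and, for responder, 2FR and 4FR status, in practice to baseline positives.

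**What to change.** In the MN50 paragraph of Section 2.1, adopt the split already used for the other assays: actual readouts above the ULOQ for immunogenicity reporting, and the cap at the ULOQ for correlates analyses only.

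If the laboratory cannot report above the ULOQ, say so and then:

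- treat those values as right-censored when estimating GMTs;
- report the share of values at the ceiling;
- show separately the baseline positives who start above ULOQ/4 (4-fold responder and 4FR) or above ULOQ/2 (2FR).

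The cost is one sentence and a small change in table code; the fallback needs somewhat more programming. The downside is that some reported MN50 values would lie above the validated range, which the SAP already accepts for the other assays.
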